## 7.8 Analysis Populations

- **Intention-to-Treat (ITT)**
- **Per Protocol (PP)**  
Both populations will be analyzed and compared

## 7.9 Software

- **SPSS Statistics v25.0** for Windows

## 7.10 Significance Threshold

- All tests two-sided
- $p < 0.05$  considered statistically significant

## 8. Ethical Considerations

- Approval granted by Ethics Committees of Área Sanitaria II and the University of Murcia.
- Informed consent obtained and signed by all participants.
- Data management adhered to Spanish data protection legislation
- Absence of prospective registry is acknowledged and will be transparently disclosed.

## 9. Study Limitations and Early Termination

Data collection was conducted over a three-years period. The final patient was enrolled and data collection for all primary and secondary outcomes, as well as adverse event monitoring, was completed in January 2017. Due to multiple logistical and operational constraints, no further patients were included after that date. Subsequently, with the emergence of the COVID-19 pandemic in December 2019, further recruitment was permanently halted. Additionally, preliminary analyses revealed that the primary outcome—the incidence of contrast-induced nephropathy (CIN) following remote ischemic preconditioning (RIPC)—did not show statistically significant differences between the intervention and control groups. These findings, combined with logistical constraints, led to the decision to halt the study before reaching the originally planned sample size. Thus, only 71 patients were enrolled—below the planned sample size. The reduced statistical power and lack of effect signal were key reasons for early termination.

**Note:** The study was not prospectively registered in a clinical trial database prior to patient enrollment. At the time of trial initiation, Spain did not have a clearly defined legal or regulatory framework mandating prospective registration for investigator-initiated interventional studies of this nature.

While Spain's Biomedical Research Law (Law 14/2007) established ethical principles and data protection standards, it did not impose a legal obligation to register non-pharmacological trials in platforms such as ClinicalTrials.gov or EudraCT. Furthermore, the regulatory provisions introduced by Royal Decree 1090/2015—which require prospective registration—apply specifically to clinical trials involving medicinal products and did not extend to procedural interventions such as remote ischemic preconditioning (RIPC). This regulatory gap, coupled with the academic nature of the study and its non-commercial scope, contributed to the lack of prospective registration.

This limitation is acknowledged and must be considered when interpreting results and assessing risk of reporting bias. The available data were analyzed and will be presented with full transparency regarding these limitations.

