## 3. Study Design

- **Type:** Randomized, parallel-group clinical trial.
- **Setting:** ICU, Hospital General Universitario Santa Lucía, Cartagena (Murcia, Spain)
- **Randomization method:** Based on sealed envelopes, using block randomization into two groups: **RIPC** and non- **RIPC**.
- **Groups:**
  - **Intervention Group:** RIPC + hydration.
  - **Control Group:** Hydration only.
- **Planned sample Size:** The sample size was determined based on data from the ARIAM registry, a Spanish national database focused on patients with acute coronary syndrome (ACS) admitted to intensive care units. According to ARIAM estimates, approximately 35–40 patients per year would meet the eligibility criteria for recruitment. It was therefore decided that the sample size would be defined by the number of patients admitted to our department with the specified characteristics during a fixed time period, establishing a convenience sampling strategy over a two-year period.
- **Actual enrolled patients:** 71.
- **Analysis population:** Both Intention-to-Treat (ITT) and Per Protocol (PP).

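### Section 9 says 71 patients fell short of a planned size and left power reduced, but Section 3 sets no target or power, and the outcome look behind the halt is undated and absent from Section 7

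*Combined protocol and SAP*

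**What the plan says.** **Section 3 (Study Design).** The planned sample size rests on a national registry estimate that "approximately 35–40 patients per year would meet the eligibility criteria for recruitment". The rule adopted on that basis reads: "sample size would be defined by the number of patients admitted to our department with the specified characteristics during a fixed time period". The length of the window is given in the same sentence: "establishing a convenience sampling strategy over a two-year period". The section gives no target number, power, control-arm rate of contrast-induced nephropathy (CIN) or detectable difference. It records 71 patients as enrolled.

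**Section 9 (Study Limitations and Early Termination).** On duration: "Data collection was conducted over a three-years period". The section dates the following to January 2017: "The final patient was enrolled and data collection for all primary and secondary outcomes". It gives a reason for enrolment ending there: "Due to multiple logistical and operational constraints, no further patients were included after that date". It then says that "with the emergence of the COVID-19 pandemic in December 2019, further recruitment was permanently halted". Next it reports that preliminary analyses found no significant difference in CIN between the groups, and that this, together with logistics, led to the decision to stop before the size originally planned. It concludes: "Thus, only 71 patients were enrolled—below the planned sample size". Reduced power and the absence of a sign of effect are named as the main reasons.

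**Section 7 (Statistical Analysis Plan).** Categorical outcomes are described by counts and percentages (7.1) and compared with a chi-square test (7.2). A covariate-adjusted logistic regression is planned to predict CIN (7.4). It names neither a treatment term nor an interval. No subsection describes an interim look or a stopping rule.

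**The concern.** A reader of Section 9 is told that the trial was cut short of a planned size and lost power as a result. Both statements need a reference value, and Section 3, where it should stand, has none. What Section 3 does contain is a time window. If the sample is whoever arrives in two years, a size that was not reached has no clear meaning.

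This affects how a non-significant CIN result is read. It may come from a truncated trial, or from a convenience sample that reached roughly the number its own plan anticipated. Those readings carry different excuses, and the documents do not let the reader choose between them. Section 9 also treats non-significance as a lack of any signal of effect, while Section 7 names no risk difference or confidence interval that would show what 71 patients can rule out.

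The order of events is a second difficulty. Between-group results on the primary outcome are said to have contributed to the halt. The look has no date, so a reader cannot tell whether enrolment ended before or after those results were seen. In a trial that was not prospectively registered, as Sections 8 and 9 acknowledge, that order should be on record.

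**Working it through.** The plan states no target number or power, so there is no figure to reproduce. The check is what Section 3 implies.

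**Inputs**
- Eligible patients per year: 35–40 (Section 3)
- Planned window: 2 years (Section 3)
- Enrolled: 71 (Sections 3 and 9)
- Duration of data collection: 3 years (Section 9)
- Last enrolment: January 2017 (Section 9)

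**Step 1: the number implied by Section 3.** Yearly eligible patients × years: 35 × 2 = 70 and 40 × 2 = 80. These are eligible patients. The plan gives no expected number enrolled and no allowance for refusal.

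**Step 2: where 71 falls.** 71 − 70 = 1 above the low end, and 71/70 = 1.01. 80 − 71 = 9 below the high end, and 71/80 = 0.89. Enrolment was thus between 89% and 101% of the eligible number anticipated.

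**Step 3: the window.** Data collection lasted three years against a planned two. With no enrolment start date, the number enrolled at two years cannot be recovered. On its face the window was probably exceeded rather than cut short.

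**Step 4: the cost in precision if the plan was 80.** With two equal arms of N/2 and event rates p₁ and p₂, the half-width of the 95% confidence interval for the risk difference is

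1.96 × √{ 2[p₁(1 − p₁) + p₂(1 − p₂)] / N }.

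At fixed rates everything except N cancels in the ratio of widths: √(80/71) = √1.127 = 1.06. The interval at 71 is about 6% wider than at 80, whatever the CIN rates. (71 cannot split evenly, so equal arms is an approximation.) Against the low end the ratio is √(70/71) = 0.99, so nothing is lost.

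**Step 5: the order of events.** Section 9 gives logistical and operational constraints for the end of enrolment in January 2017, the pandemic for the permanent halt of recruitment, and the preliminary analyses combined with logistics for the decision to stop. If the look came after January 2017, it could not have ended enrolment then. If it came earlier, the outcome may have informed the stop. Neither Section 7 nor Section 9 settles which.

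**The case against.** The strongest reply is that Section 9 may be right. Of the eleven whole numbers from 70 to 80, nine exceed 71, so being below plan is compatible with Section 3. That stands. A reader might infer that the shortfall statement is false, and the documents do not support that: it is unsupported, not disproved. A target may have existed outside this document.

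A reader might also multiply the yearly figure by the three years of data collection and infer a large shortfall. No section states a three-year plan. Section 3 says two years, so the documents give no basis for a shortfall of that kind.

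Nor can absolute power be stated. It would rest on control rates and effects that the documents do not give.

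It can be said that Section 9 already discloses the small sample, the look and its part in the halt, and gives a reason for no enrolment after January 2017. That is fair. The look is called unplanned here only because Section 7 does not mention one. A reader might infer that the null result ended enrolment, or that type I error was inflated. The undated account does not establish the first, and stopping on a non-significant result does not by itself produce the second.

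Finally, CIN analysis is not limited to a chi-square test, since Section 7.4 plans a logistic regression, and an interval could be computed from the planned counts. Both points are true. Section 7 still does not commit to an estimate of the group difference with an interval.

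**Conclusion.** The concern holds in a limited form and should be fixed. The statements that 71 is below a planned size and that power was reduced have no stated reference and are in tension with Section 3, whose own rule implies 70–80 eligible patients over two years. The gap lies between 1 above and 9 below that range. If 80 is taken as the plan, the interval is about 6% wider. This assumes equal arms, unchanged event rates and enrolment of every eligible patient. The missing patients can therefore explain little of an inconclusive result when judged against Section 3.

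Separately, an outcome look that Section 7 does not describe, made without any stated rule, is credited with part of the halt and is not placed in time relative to the last enrolment. Its role cannot be determined from the documents. None of this changes the primary test. It changes what a reader may conclude from a non-significant result.

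**What to change.** 1. **Reconcile Sections 3 and 9 on size.** If a numeric target existed, state it with its basis, and say what the reduced power was measured against. If none existed, replace the shortfall and reduced-power statements with wording such as: *71 enrolled; Section 3 anticipated about 70–80 eligible patients over two years; no power-based target was set.* Reword the stopping reason to match.
2. **Document the look.** Report the preliminary analysis as one that Section 7 does not describe and that was made without a stopping rule. Give its date relative to the last enrolment in January 2017.
3. **Report what the data can rule out.** Give the CIN risk difference between groups with its 95% confidence interval. Interpret a non-significant result from that interval, not as lack of effect or as the product of a truncated trial.

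The cost is rewording in two sections, facts the sponsor should hold (any original target, the date of the look) and one interval from the existing two-by-two table. The downside is that the stated explanation for the small sample becomes slightly less favourable.

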## 2. Objectives

### Primary Objective

- To evaluate the impact of RIPC on the incidence of CIN in diabetic patients undergoing coronary catheterization, using serum creatinine, as biomarkers.

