## 6. Outcome Measures

### **Primary Endpoint**

- CIN defined as either a 25% increase in serum creatinine (SCr) from baseline or a 0.5 mg/dL increase in absolute SCr value—within 72 hours after intravenous contrast administration.

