## 7. Statistical Analysis Plan (SAP)

### **7.1 Descriptive Statistics**

- **Qualitative variables:** Presented as frequencies and percentages per group/subgroup.
- **Quantitative variables:** Described using minimum, maximum, mean, and standard deviation.

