## 7.2 Univariate Analysis

- **Qualitative comparisons:** Chi-square test.
- **Quantitative comparisons:** Student's T-test, after verifying:
  - **Normality:** Shapiro-Wilk test.
  - **Homogeneity of variances:** Levene test.
- If assumptions are violated: Mann-Whitney U test will be used.

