## 7.4 Multivariate Analysis

- **Binary logistic regression** to predict CIN occurrence, adjusted for covariates.

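### The SAP names no between-arm estimate or confidence interval for CIN and no primary population, and Section 9 cites non-significance in 71 patients as a lack of effect signal

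*Combined protocol and SAP*

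**What the plan says.** The primary objective (Section 2) is "To evaluate the impact of RIPC on the incidence of CIN in diabetic patients undergoing coronary catheterization". The endpoint (Section 6) is binary: within 72 hours of contrast, "either a 25% increase in serum creatinine (SCr) from baseline or a 0.5 mg/dL increase in absolute SCr value".

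The planned outputs for such a variable are:

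- Section 7.1: "Presented as frequencies and percentages per group/subgroup".
- Section 7.2: "Chi-square test" for qualitative comparisons. CIN is not named there, but it is a qualitative variable and so falls under this rule.
- Section 7.4: binary logistic regression "to predict CIN occurrence, adjusted for covariates". The covariates are not listed, and randomised treatment is not stated to be a term.
- Section 7.10: two-sided tests with a 0.05 threshold.

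No risk difference, risk ratio, odds ratio or confidence interval is specified anywhere. Sections 3 and 7.8 list both ITT and PP without saying which is primary.

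Section 9 reports that preliminary analyses found no statistically significant difference in CIN between the groups. It also describes logistical constraints, and ends that paragraph with: "The reduced statistical power and lack of effect signal were key reasons for early termination".

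**The concern.** The objective asks how much RIPC changes the incidence of CIN. The plan answers with two percentages and a p-value, and no planned output shows which sizes of effect the data exclude.

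That gap matters because the only efficacy finding in Section 9 is non-significance, and the same section treats it as a lack of effect signal. In a trial of this size non-significance is compatible with a useful benefit, with no effect or with harm. If the report follows the plan, the stopping reason may be carried forward as evidence that RIPC does not work in diabetic patients, with no interval to check it against.

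Leaving ITT and PP unranked adds to the problem: if the two differ, the plan does not say which answers the primary objective.

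**Working it through.** The plan gives no power, target effect, CIN rate or event count, so there is no figure of its own to reproduce. What follows is an illustration on stated assumptions.

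**Inputs**

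- From the documents: 71 patients, two arms (Sections 3 and 9); chi-square test (7.2); two-sided 0.05 (7.10).
- Assumed: 36 RIPC v 35 control, because the allocation ratio is not stated; control CIN rate 10 to 40%; a halving of CIN as the reference effect.

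**Step 1. Power of the planned test for a halving.** Exact power is the sum of Bin(a; 36, p/2) × Bin(b; 35, p) over all tables (a, b) whose Pearson chi-square, without continuity correction, exceeds 3.84.

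| Control rate p | RIPC rate p/2 | Power | Chance of non-significance |
|---|---|---|---|
| 10% | 5% | 12% | 88% |
| 15% | 7.5% | 17% | 83% |
| 20% | 10% | 21% | 79% |
| 30% | 15% | 32% | 68% |
| 40% | 20% | 45% | 55% |

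Check at 20% by the normal approximation:

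- Pooled rate = (36×0.10 + 35×0.20)/71 = 0.149.
- Null SE = √[0.149×0.851×(1/36+1/35)] = 0.0846.
- Alternative SE = √[0.10×0.90/36 + 0.20×0.80/35] = 0.0841.
- Power ≈ Φ[(0.10 − 1.96×0.0846)/0.0841] = Φ(−0.78) ≈ 0.22, in line with the exact 21%.

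Uneven splits of 40 v 31 or 31 v 40 give 10 to 49% over the same control rates. Across the assumed range, non-significance is the likelier outcome even if RIPC truly halves CIN.

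**Step 2. What a given p-value leaves open.** Take 7/35 control events (20%) and two hypothetical RIPC results.

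- Risk ratio interval: exp[ln RR ± 1.96 × SE], with SE = √(1/a − 1/36 + 1/b − 1/35).
- Risk difference interval (Newcombe): with Wilson limits l and u for each arm, d − √[(p₁−l₁)² + (u₂−p₂)²] to d + √[(u₁−p₁)² + (p₂−l₂)²].
- Wilson limits: 7/35, 0.100 to 0.359; 4/36, 0.044 to 0.253; 11/36, 0.180 to 0.469.

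| RIPC v control | Percentages | p | RR (95% CI) | RD, points (95% CI) |
|---|---|---|---|---|
| 4/36 v 7/35 | 11% v 20% | 0.30 | 0.56 (0.18 to 1.73), SE 0.580 | −8.9 (−26.1 to +8.5) |
| 11/36 v 7/35 | 31% v 20% | 0.31 | 1.53 (0.67 to 3.49), SE 0.421 | +10.6 (−9.7 to +29.7) |

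The p-values are almost the same. The percentages already show that the two results point in opposite directions. Only the intervals show that the first leaves a risk ratio of 0.5 open and the second does not.

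**Step 3. The scale matters.** For 14/36 v 14/35 the RR interval is 0.55 to 1.73, which excludes a halving. The RD interval is about −23 to +21 points, which includes a 20-point fall, half of 40%. A statement about a relative reduction therefore has to rest on the risk-ratio interval.

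**The case against.** The strongest reply is that Section 9 does not claim proof of no effect. The phrase is a reason for stopping. It stands beside admitted low power and logistical constraints, in a section that calls itself a statement of limitations and promises transparency. This stands: a reader might infer that the trial has formally concluded RIPC is ineffective, and the text does not say so. Nor does it say that a p-value was all that was examined; non-significance is simply all that is reported. But admitting low power does not rescue the phrase, because low power is why non-significance says little about effect.

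Second, Section 7.1 requires counts and percentages per group, so readers will see the direction of the difference and could work out an interval themselves. That also stands. It would be wrong to say that a report following the plan hides whether RIPC did better or worse. What remains is that the plan does not specify the interval, or say whether the ITT or the PP table is the one to use.

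Third, the logistic model could yield an adjusted odds ratio for treatment. It could, but only if treatment is in the model, and Section 7.4 describes prediction of CIN without saying that it is.

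Finally, every rate, split and event count in the illustration is assumed. That is so, and it limits what can be said about the actual result.

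**Conclusion.** The point holds for the plan and for the wording of Section 9. The SAP specifies no between-arm estimate, no confidence interval and no primary population for CIN, and non-significance in 71 patients does not by itself support the effect-signal phrase. With 36 v 35 patients and control rates of 10 to 40%, all assumed, the planned test has only 12 to 45% power for a halving.

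A reader might go further and infer that the trial's result is inconclusive. The documents do not support that either: they give no event counts, and some non-significant tables do exclude a halving on the risk-ratio scale (11/36 v 7/35 and 14/36 v 14/35 above). The interval from the actual data has to decide.

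This should be fixed before results are reported. It does not invalidate the trial.

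**What to change.** 1. In 7.2 and 7.8, make the ITT comparison primary and PP a sensitivity analysis. Beside the chi-square p-value, report the CIN risk difference, RIPC minus control, with a 95% interval suited to small counts (for example Newcombe), and the risk ratio with its 95% interval. Use the risk-ratio interval for any statement about a relative reduction such as a halving.
2. In 7.4, if the logistic model is used for the treatment effect, include the treatment term, report its odds ratio with 95% interval, and keep the covariates few and named.
3. In Section 9, keep the historical stopping reason as a matter of record. Add the estimate and interval, state which effects are not excluded, and do not present non-significance as lack of effect. Call the result inconclusive only if the interval spans both a useful benefit and no benefit or harm.
4. Label each addition in the SAP and report as made after the preliminary between-arm look.

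The cost is a few SAP lines, one re-analysis of data already held, and a reworded passage in Section 9; the unadjusted intervals come straight from the 2×2 table. The downside is that the additions are post-look and must be shown as such, and that a negative reading may turn into an inconclusive one.
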